### 9.2.5.3 Exploratory analyses

The possible effect of previous seasonal influenza vaccination, age, presence of detectable levels of antibody before vaccination, as well as vaccine type – and any interactions will be explored using (generalised) linear models.

If one vaccine is available significantly before the other, then the trial will adopt a sequential allocation procedure switching to randomisation when the second one becomes available. If such a situation arises then the comparisons outlined in 9.2.5.1 will be non-randomised ones and potentially subject to bias (for example due to temporal effects). In this situation the use of date (time) of vaccination will also be used as an explanatory covariate in (generalised) linear models in order to explore the potential impact of this on the trial outcomes.

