**9.2.5 Immunogenicity objectives**

**9.2.5.1 Primary immunogenicity objective**

The primary immunogenicity objective is to evaluate the immunogenicity of Baxter cell-culture, non-adjuvanted, whole virus H1N1 vaccine, and GSK AS03-adjuvanted, split H1N1 vaccine with respect to Committee of Human Medicinal Products (CHMP) and FDA licensing criteria.

These criteria for adults aged between 18 and 60 years are, for sera collected ‘approximately 3 weeks after vaccination’:

- Number of seroconversions or significant increase in antihaemagglutinin antibody titres >40%
- Mean geometric increase >2.5
- The proportion of subjects achieving an HI titre of  $\geq 40$  or SRH titre of  $25 \text{ mm}^2$  should be >70%

For adults aged over 60 years these criteria are:

- Number of seroconversions or significant increase in antihaemagglutinin antibody titres >30%
- Mean geometric increase >2.0
- The proportion of subjects achieving an HI titre of  $\geq 40$  or SRH titre of  $25 \text{ mm}^2$  should be >60%

The measures of immunogenicity will be calculated as:

*Geometric Mean Titre or Geometric Mean Area:* For each vaccine/age group and each vaccine type, least squares GMTs for HI and MN data (GMAs for SRH data), associated 95% confidence interval and median, minimal, and maximal titre value will be determined for each visit, i.e., days 0, 7, 14, 21, 28, 35, 42, and 180.

**Geometric Mean Ratio (increase):** For each vaccine/age group and each vaccine type, the least squares GMRs will be calculated for the HI, MN and SRH results for the following time points of the study: day 7/day 0, day 14/day 0, day 21/day 0, day 28/day 0, day 35/day 0, day 42/day 0, as well as the associated 95% confidence intervals and the median, minimal, and maximal n-fold increase. Statistical methods used to analyze GMRs will be identical to those described above for GMTs (GMAs).

**Seroconversions:** Percentages of subjects with seroconversion (or significant increase in HI titre). The number and proportion of subjects achieving seroconversion or significant increase in HI titres or SRH area from pre-immunization to each visit after first immunization will be tabulated for each vaccine/age group and each age group.

- Seroconversion is defined as negative pre-vaccination serum (<10 for HI, <4 for SRH) / positive post-vaccination titre ( $\geq 40$  for HI, area  $\geq 25 \text{ mm}^2$  for SRH).

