- Significant increase in antibody titre/area is defined as at least a fourfold increase in HI or a 50% increase in area from non-negative pre-vaccination serum ( $\geq 10$  for HI,  $\geq 4$  for SRH).

**Seroprotection:** Percentages of subjects achieving each of the following thresholds: inverse HI titre  $\geq 40$ , SRH area  $\geq 25 \text{ mm}^2$ : The number and proportion of subjects achieving each threshold at each visit will be tabulated for each vaccine/age group and each vaccine type.

All statistical analyses for HI and SRH will be performed on the logarithmically (base 10) transformed values. Titres below the limit of detection for assays will be set to 1 in 5 for HI and  $4 \text{ mm}^2$  for SRH for the purposes of analysis. Original values will be presented in all listings

The above immunogenicity criteria will be applied to sera collected 21 days after completion of vaccination, i.e., 21 days after the second vaccine dose. For pandemic vaccines, all three criteria should be met.

Should both GSK and Baxter vaccines satisfy all three CPMP criteria, we will compare the immunogenicity of the two vaccines (for each vaccine/age group and each vaccine type) in terms of:

- a. Geometric mean titres 21 days after each vaccination;
- b. Geometric mean ratio increases 21 days after each vaccination;
- c. Seroprotection rates 21 days after each vaccination;
- d. Seroconversion rates 21 days after each vaccination.

Comparisons will be made using parametric or non-parametric tests as appropriate for continuous outcomes, and Pearson's chi-square test or Fisher's exact test where appropriate for categorical outcomes. Further analyses using (generalised) linear models will explore the effect of baseline covariates on the outcomes. For populations (a) and (b), analyses using multiple imputation to allow for missing data will also be undertaken as a sensitivity analysis. No formal adjustment will be made for multiple testing but associated P-values will be interpreted cautiously.

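### For seroconversion, the coefficient for detectable pre-vaccination antibody is mixed with the endpoint definition, because the responder rule changes at the same HI cut-off of 10

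*Protocol*

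**What the plan says.** Section 9.2.5.3 of the protocol lists the factors to be explored: previous seasonal vaccination, age, "presence of detectable levels of antibody before vaccination, as well as vaccine type". It adds that "any interactions will be explored using (generalised) linear models". It does not name the outcome of these models.

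Section 9.2.5.1 lists four outcomes for comparing the vaccines 21 days after each dose: geometric mean titre, geometric mean ratio, seroprotection rate and seroconversion rate. It then says: "Further analyses using (generalised) linear models will explore the effect of baseline covariates on the outcomes". Section 9.2.5.2 repeats this for the secondary measures.

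The responder definition in 9.2.5.1 has two branches:

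- **Undetectable at baseline:** "Seroconversion is defined as negative pre-vaccination serum (<10 for HI, <4 for SRH) / positive post-vaccination titre", where positive means HI of at least 40 or an SRH area of at least 25 mm².
- **Detectable at baseline:** "at least a fourfold increase in HI or a 50% increase in area from non-negative pre-vaccination serum".

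On values below detection the same section says: "Titres below the limit of detection for assays will be set to 1 in 5 for HI" (and 4 mm² for SRH).

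**The concern.** The yes/no covariate and the switch between the two branches of the responder definition are the same variable. A subject with an undetectable Day 0 titre faces a higher hurdle than one with a detectable titre. A model of seroconversion on detectability therefore estimates two things at once: any real influence of existing antibody, and the difference in hurdle. Nothing in the protocol warns of this.

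The subject is of practical interest. Section 4.0 raises the possibility that one dose may be enough in older people, and says that cross-reacting antibody becomes more common with age. Under 9.2.7, interim results go to the Department of Health to inform vaccination strategy. A coefficient that could be strongly positive or clearly negative without any real difference in the quantity of interest is a poor guide to how baseline antibody affects response. The yes/no coding also treats a baseline of 10 and a baseline of 640 alike.

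**Working it through.** **Inputs from the protocol (9.2.5.1):** cut-off HI 10; assigned value 5 below it; target 40 if undetectable; fourfold rise if detectable. SRH: cut-off 4, assigned 4 mm², target 25 mm², or a 50% rise. Size (9.2.1): six groups of 60 with at least 50 evaluable, so about 6 × 50 = 300 evaluable.

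**Inputs not in the documents (assumed, shown as ranges):** distribution of the fold rise, distribution of baseline titres, assay error, and the proportion detectable by HI. The protocol states no figure for the effect of baseline antibody, so there is none to reproduce.

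**Step 1: the two hurdles on the analysis scale.**

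- HI: 40/5 = 8-fold if undetectable, 4-fold if detectable.
- SRH: 25/4 = 6.25-fold if undetectable, 1.5-fold if detectable.

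The 8 follows from the assigned value 5. A true baseline just under 10 needs just over 4-fold (40/9.99 = 4.004), and one below 5 needs more than 8-fold. The hurdle for undetectable subjects is always above 4-fold.

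**Step 2: equal fold rise at every baseline.** Let log10 fold rise be normal with median m and SD s, the same for everyone, and let undetectable equal 5. Then

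- P(responder | undetectable) = 1 − Φ((log10 8 − log10 m)/s)
- P(responder | detectable) = 1 − Φ((log10 4 − log10 m)/s)

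| m | s | Undetectable | Detectable | OR |
|---|---|---|---|---|
| 4 | 0.5 | 27.4% | 50.0% | 2.66 |
| 8 | 0.4 | 50.0% | 77.4% | 3.43 |
| 8 | 0.5 | 50.0% | 72.6% | 2.66 |
| 8 | 0.6 | 50.0% | 69.2% | 2.25 |
| 16 | 0.4 | 77.4% | 93.4% | 4.12 |
| 16 | 0.6 | 69.2% | 84.2% | 2.37 |

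Over m = 4 to 16 and s = 0.4 to 0.6 the OR runs from 2.2 to 4.1. With 300 evaluable and 10, 20 or 30% detectable, the two-proportion formula gives p < 0.05 in 67, 90 and 96% of trials at m = 8, s = 0.5. At m = 16, s = 0.6 the figures are 38, 66 and 80%.

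**Step 3: other meanings of no effect.** Simulation with baseline median 5 or 7, log10 SD 0.4, duplicate twofold dilutions, assay error SD 0 or 0.15, and a fold rise of 5, 10 or 20:

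| Relation of post-vaccination titre to baseline | Detectable minus undetectable | OR |
|---|---|---|
| Equal fold rise | +23 to +43 points | 3.8 to 12.8 |
| Half the baseline log difference carries over | +7 to +19 points | 1.5 to 2.6 |
| Post-vaccination titre unrelated to baseline | −6 to −16 points | 0.46 to 0.74 |

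The odds ratios in the first row exceed those in Step 2 because true baselines below 5 and coarse dilutions raise the hurdle for undetectable subjects further.

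In the half-carry-over case, two of the protocol's outcomes point in opposite directions. With baseline median 5, a fold rise of 10 and error SD 0.15, seroconversion is 61.9% in detectable and 47.1% in undetectable subjects, while the observed geometric mean ratio is 4.7 against 6.0.

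Rejection rates of a chi-square test at 5% for those settings, with n = 100, 150 and 300:

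- equal fold rise: 88, 96 and over 99%, all positive;
- half carry-over: 19, 29 and 52%, positive;
- unrelated to baseline: 14, 21 and 38%, essentially all negative.

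**Step 4: the alternative model.** With log10 post-vaccination titre regressed on log10 Day 0 titre plus an indicator for undetectable, and a true slope of 1 (equal fold rise), the simulated slope among detectable subjects was 0.92 to 0.97.

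**The case against.** The strongest case on the other side is that the plan only explores a possible effect, that 9.2.5.3 names no outcome, and that geometric mean titre stands first in the 9.2.5.1 list, with HI and SRH analysed on the log10 scale. The better analysis is thus already allowed, and the choice of outcome and coding is often left to a statistical analysis plan. Much of this stands, and it limits the weight of the point. It does not remove it: the protocol itself fixes a yes/no covariate at the endpoint's own switch point and includes seroconversion among the outcomes. The promise to interpret P-values cautiously concerns multiple testing, not this.

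A reader might infer four stronger things that the documents do not support.

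- **That the plan will show a false priming effect in almost any data set.** The sign depends on what no effect means, and the protocol does not say. Even with equal fold rises, significance can fall to 38% of trials in the range examined.
- **That all the outcomes share the defect.** The rule switch touches seroconversion only. A Day 0 titre of 40 or more does already meet the seroprotection threshold, but that is a property of the endpoint. Substituting 5 distorts the fold rise in either direction: too small if the true titre is below 5, too large if it lies between 5 and 10.
- **That the one-dose question is compromised.** Section 9.2.5.2a settles it from the criteria after dose one, without a covariate model.
- **That the age effect must be distorted.** Age and detectability are listed together in 9.2.5.3. The figures in section 4.0 (33% at 60 and over against 6% at 18 to 40) are microneutralisation titres of at least 160, not HI detectability.

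**Conclusion.** The point holds for seroconversion in the covariate models. The detectability coefficient cannot be separated from the difference between an 8-fold and a 4-fold hurdle, both of which follow from the protocol's own values. Its size and sign depend on assumed titre distributions: OR about 2.2 to 4.1 if the fold rise is the same at every baseline, and about 0.6 if the post-vaccination titre is unrelated to baseline. Between these, seroconversion and fold rise can contradict each other. The analysis is exploratory and the licensing verdicts do not depend on it. This is therefore a cheap improvement to an analysis that would otherwise give an uninterpretable result, and not a threat to the trial's main conclusions.

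**What to change.** In 9.2.5.3, assess the effect of pre-vaccination antibody mainly with log10 Day 21 and Day 42 titre as the outcome. Enter log10 Day 0 titre as a continuous covariate plus an indicator for undetectable, or use a method that handles censoring below 10.

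Seroconversion may still be tabulated by baseline status. Baseline antibody may still serve as an adjustment covariate in the vaccine comparisons of 9.2.5.1 and 9.2.5.2, which matters more if allocation turns out to be sequential and non-randomised, as 9.2.5.3 foresees. Add one sentence saying that the detectability coefficient for seroconversion is not to be interpreted as a biological effect.

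The cost is wording only, since all values are already collected. There are two small downsides. The baseline effect is reported on the titre scale and not as a difference in responder rates. The slope is also somewhat affected by assay error and coarse dilutions (0.92 to 0.97 in simulation where the truth was 1), so it should not be tested strictly against 1.

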### 9.2.6 Analysis of local and systemic symptoms and adverse events

For the purpose of data partitioning and analysis, the study will be partitioned into the following broad time intervals to compare short term reactogenicity to vaccination:

- Vaccination to 48 hours;
- 48 hours to 7 days and
- Beyond 7 days.

Analysis will focus on comparisons of the incidence and severity of local and systemic reactions as indicated by the presence of specific symptoms, symptom scores, and temperature elevations.

#### 9.2.6.1 Local and systemic symptoms

The incidences of local and systemic reactions following vaccination will be summarized by vaccine group.

The occurrence of selected indicators of reactogenicity (listed below), which by definition, can only occur up to 6 days post-vaccination, will be recorded on the Local and Systemic Reactions Diary/CRF rather than the Adverse Events CRF.

- Local reactions: Ecchymosis, erythema, induration, swelling and pain at injection site.
- Systemic reactions: Chills, malaise, myalgia, arthralgia, nausea, headache, sweating and fatigue
- Other indicators of reactogenicity: Stayed at home due to reactions, oral temperature, and use of analgesic/antipyretic medication.

If a reaction occurs more than once for a subject, the reaction will be classified according to the highest occurring severity.

All study subjects will be observed for at least 30 minutes after a vaccination for evidence of immediate reactions in general and in particular for symptoms of allergic phenomena (such as rashes, itching, or other allergic manifestations).

Each subject will be instructed to complete a diary card for 7 days following each vaccination, to describe local and systemic reactions and other selected indicators of reactogenicity. If a local and systemic reaction or fever (derived from measured oral temperatures  $\geq 38.0^{\circ}\text{C}$ ) continues beyond the 7-day period after a vaccination, it will also be recorded on the Adverse Events CRF. If the subject recovers on the last day, then this fact will be recorded on the Local and Systemic Reaction CRF.

We will summarise the occurrence of solicited local and systemic symptoms (point estimates and 95%CI) by vaccine type in terms of incidence, intensity, and relation to vaccination. We will use the two-sided Fisher's exact tests to compare groups where appropriate.

Frequencies and percentages (together with 95% CIs) of subjects experiencing each reaction will be presented for each symptom severity. Summary tables showing the occurrence of any local or systemic reaction overall and at each time point will also be presented.

The severity of local reactions, including injection-site ecchymosis, erythema, swelling, and induration, will be categorized as none, 1 to  $\leq 25$  mm, 26 to  $\leq 50$  mm and  $> 50$  mm.

The severity of pain and systemic reactions will be categorized as none, mild (transient with no limitation in normal daily activity), moderate (some limitation in normal daily activity), and severe (unable to perform normal daily activity).

Distribution of body temperature, staying at home due to vaccine reaction and the use of analgesic/antipyretic medication occurring during 7 days after each vaccination will be tabulated. Fever will be defined as a temperature of  $\geq 38.0^{\circ}\text{C}$ , and severe fever as  $\geq 40.0^{\circ}\text{C}$ . Oral temperature will be categorized as  $< 38^{\circ}\text{C}$ ,  $38^{\circ}\text{C}$  to  $< 39^{\circ}\text{C}$ ,  $39^{\circ}\text{C}$  to  $< 40^{\circ}\text{C}$ , and  $\geq 40^{\circ}\text{C}$ .

All post-vaccination reactions (local and systemic), use of relief medication and absence from work due to any adverse events will be summarized as none *versus* any.

For the local and systemic reaction safety variables, differences among the groups after vaccination will be analyzed by using Pearson's chi-square test or Fisher's exact test where appropriate.

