#### **Visit 1: Day 0: Screening and first vaccination**

1. Subjects will be enrolled providing they meet inclusion and exclusion criteria and give fully informed, written consent.
2. For females of childbearing potential, perform a urine pregnancy test.

3. If the subject meets all the inclusion criteria and none of the exclusion criteria, assign a study subject number relevant to the subject's age and study centre (for further information please refer to paragraph 7.4.).
4. Obtain basic demography, including age, sex, ethnicity, previous influenza vaccination (past three seasons), and influenza-like illness (since May 2009).
5. Obtain and record significant medical history.
6. Record any current medications taken. Verify if the subject has taken an analgesic/antipyretic medication on Day 0 prior to study vaccination. Document this information on the subject's appropriate CRF.
7. Collect 10ml clotted blood pre-immunisation for baseline antibodies. Process blood and store serum for serology assays as described in section 8.2.
8. Record oral temperature.
9. The vaccine administrator will give vaccine according to the randomisation list (if GSK and Baxter vaccines are both available) by IM injection in the deltoid muscle of the upper non-dominant arm.
10. Examine the site of injection of the vaccine for local reactions at the end of 30 minutes. These findings and any systemic reactions will be recorded on the appropriate CRF page.
11. Instruct each subject in the evaluation of local and systemic reactions (e.g. how to measure the maximum diameter of induration and erythema in millimetres at the injection site and how to record temperature with a thermometer). As a guide for subsequent evaluations, enter the findings from the 30-minute post-injection evaluation onto the subject diary card.
12. Give the subject diary card and thermometer for immunisation reactions to subjects and instructions for its completion. Tell subjects to:
  - Complete the diary at approximately the same time each day;
  - Notify study personnel immediately if the subject experiences a SAE. Serious adverse events are defined in Sections 1.2 and 8.5
  - Return the diary card to the site on the Day 7 visit.
13. Schedule the Day 7 visit.

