### **8.3 Diary cards**

Diary cards will be issued to all subjects instructing them to record their temperature and local and systemic symptoms at 6 and 24 hours after vaccination, and then daily for a total of 7 days, or longer should symptoms persist.

Information will be sought concerning the presence or absence of: redness at the injection site; local itching; local swelling; ulceration at the injection site; local pain; warm feeling at the injection site; tenderness to touch at the injection site; limitation of the use of the arm; headache; nausea; dizziness; diminished appetite; breathlessness; cough; coryza; wheeze; skin rash; generalised itching; fatigue; 'other' symptoms, use of antipyretic/relief medication and any changes in medication.

Subjects will score the severity of symptoms and effect on daily activities ranging from 0 (symptom absent), 1 (symptom occurred but not often or severe enough to cause inconvenience), 2 (symptom occurred often and severe enough to interfere with daily activities and requires no medical intervention), 3 (symptom occurred often, severe enough to markedly interfere with daily activities; requires medical intervention).

Subjects will also be asked to document any unsolicited symptoms.

Subjects will be instructed that in the event of any serious adverse event, he/she must notify the investigator immediately and be reviewed clinically. Serious adverse events are defined in (see Definitions (Sections 1.2 and 8.5).

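### The diary list in section 8.3 omits 7 of the 13 reactions named for analysis (6 if induration is credited), and its severity score departs from the analysis scale at the top grade and for size-graded local reactions

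*Protocol*

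**What the plan says.** **Reactions to be analysed.** Section 9.2.6.1, repeating the list in section 8.4, names "Local reactions: Ecchymosis, erythema, induration, swelling and pain at injection site" and "Systemic reactions: Chills, malaise, myalgia, arthralgia, nausea, headache, sweating and fatigue". Section 8.4 sends them to a dedicated reactions CRF and section 9.2.6.1 to a combined diary/CRF. Section 9.2.6.1 also makes the seven-day diary card the means by which subjects describe these reactions, and promises point estimates and 95% confidence intervals for solicited symptoms by vaccine.

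**Symptoms the diary asks about.** Section 8.3 lists, for the injection site, "redness at the injection site; local itching; local swelling; ulceration at the injection site; local pain; warm feeling at the injection site", then tenderness and limited use of the arm. The remaining items are "headache; nausea; dizziness; diminished appetite; breathlessness; cough; coryza; wheeze; skin rash; generalised itching; fatigue; 'other' symptoms". Temperature, relief medication and changes in medication are also recorded.

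**Severity.** Section 8.3 has subjects score each symptom 0 to 3. Grade 3 is "severe enough to markedly interfere with daily activities; requires medical intervention", while grade 2 interferes with activity but needs no medical intervention. Section 9.2.6.1 grades pain and systemic reactions by limitation of activity alone, the top category being "severe (unable to perform normal daily activity)". It grades ecchymosis, erythema, swelling and induration in millimetre bands with cut points at 25 and 50 mm.

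**Measurement training.** Visit 1 in section 8.1 teaches subjects "how to measure the maximum diameter of induration and erythema in millimetres at the injection site", and Visit 4 repeats this.

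**The concern.** Short-term reactogenicity is a secondary objective (section 5.0). It also feeds the interim reports meant to inform Department of Health strategy (section 9.2.7), in a head-to-head comparison of an AS03-adjuvanted with a non-adjuvanted vaccine. Section 9.2.6 says the analysis will focus on the incidence and severity of specific symptoms.

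An incidence for a solicited reaction presumes that every subject was asked about it. A reaction that is not on the card can enter only if the subject volunteers it under the free-text item or as an unsolicited symptom. Such counts risk being too low, and they should not be tabulated beside reactions that every subject was asked about. Both vaccines use the same card, so the gap does not by itself favour either. It does weaken the comparison for exactly the items affected.

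The severity tables raise a second problem: the grade recorded and the grade to be reported are defined on different grounds.

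**Working it through.** The protocol states no figure to reproduce here. The check is an item-by-item match, followed by a comparison of the scales.

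**Step 1: match the lists** (section 9.2.6.1 against section 8.3, taking erythema as redness).

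| Reaction to be analysed | Diary item in 8.3 |
|---|---|
| Ecchymosis | none |
| Erythema | redness |
| Induration | none (but see step 2) |
| Swelling | local swelling |
| Pain | local pain |
| Chills | none |
| Malaise | none |
| Myalgia | none |
| Arthralgia | none |
| Nausea | nausea |
| Headache | headache |
| Sweating | none |
| Fatigue | fatigue |

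- Analysis list: 5 local + 8 systemic = 13.
- Matched: 3 local + 3 systemic = 6.
- Not on the diary list: 13 − 6 = 7 (7/13 = 54%), made up of 2 of 5 local and 5 of 8 systemic.

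**Step 2: credit induration.** Subjects are trained at Visits 1 and 4 to measure it, and at Visit 1 the 30-minute findings are copied onto the card. If that counts as solicitation, 6 of 13 are missing (46%) and 1 of 5 local. The systemic count stays at 5 of 8.

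**Step 3: the reverse match.** The diary names 8 local + 11 other = 19 symptoms, and 19 − 6 = 13 of them are not among the named reactions.

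**Step 4: severity of pain and systemic reactions.**

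| Diary score (8.3) | Analysis category (9.2.6.1) | Agreement |
|---|---|---|
| 0, absent | none | yes |
| 1, no inconvenience | mild, activity not limited | roughly |
| 2, interferes; no medical intervention | moderate, some limitation | roughly |
| 3, marked interference; medical intervention | severe, unable to carry on normal activity | no |

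A subject who could not carry on normal activity and needed no medical intervention is severe in the analysis. On the card that subject fails the medical clause of grade 3, and the wording of grade 2 is the only one that fits on that clause. Section 8.5 adds a third scale for adverse events, in which severe requires both inability and medical attention. Reactions that last beyond seven days are also recorded on the adverse events form, so one reaction can be graded under two definitions.

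**Step 5: size-graded local reactions.** Four reactions need a diameter. A 0–3 score cannot give one. The training text names two of the four (erythema and induration), and swelling and ecchymosis have no stated measurement.

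**The case against.** The strongest reply is that the card and the CRF themselves are not shown. Section 8.3 only describes the card, staff review it at Days 7 and 28, and the reactions CRF may prompt for the missing items. That limits the claim to what the protocol states. It does not remove the contradiction: if the card asks more than section 8.3 says, section 8.3 misdescribes it. No visit procedure describes asking about the missing reactions, and a statistical analysis plan cannot supply answers to questions that were not put.

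Several stronger readings are tempting but not supported:

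- *The reactogenicity comparison cannot be made at all.* Six reactions, temperature and relief medication are on the card. The none-versus-any summary in section 9.2.6.1 needs no severity scale.
- *The two severity scales have nothing in common.* Both have four ordered levels and the lower three correspond roughly. The gaps are the top level and the millimetre bands.
- *Severe reactions will be under-counted.* The wording makes this plausible, but the documents give no figure for it. Staying at home and absence from work are tabulated separately and would partly pick up such subjects.
- *The 13 diary-only symptoms will go unanalysed.* Section 9.2.6.1 also summarises solicited symptoms and all post-vaccination reactions in general terms. Asking about more symptoms than the named indicators is not an error.
- *The loss is final once the first cards come back at Day 7.* A second card is issued at Day 21, so a corrected card could still cover dose 2. Reliable solicited data for dose 1 would be missing for subjects already past it.

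**Conclusion.** The concern holds as an internal contradiction confined to part of the reactogenicity analysis. Section 8.3 omits 7 of the 13 reactions that sections 8.4 and 9.2.6.1 name, or 6 if induration is credited through the measurement training. Five of the 8 systemic reactions are unsolicited on either count. The diary score disagrees with the analysis scale at the top level and cannot give the millimetre bands. The comparison of the six matched reactions stands on incidence. The comparison of all 13 on incidence and severity cannot be made as described.

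This rests on two assumptions: that section 8.3 describes the card completely, and that redness is the diary's term for erythema. The size of any under-ascertainment cannot be derived from the documents. The point should be corrected, because it affects a secondary objective and the interim reports, and the correction is cheap before enrolment.

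**What to change.** Before first enrolment:

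1. Use one reaction list in sections 8.3, 8.4 and 9.2.6.1, adding ecchymosis, induration, chills, malaise, myalgia, arthralgia and sweating to the diary card.
2. Add fields for maximum diameter in millimetres for erythema, swelling, induration and ecchymosis, and extend the training text at Visits 1 and 4 to all four.
3. Use one severity scale in the diary and the analysis for pain and systemic reactions, and record medical attention as a separate yes/no item.
4. State in section 9.2.6.1 how the diary symptoms outside the named list will be summarised.

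The cost is a reprinted, slightly longer card and the alignment of a few paragraphs. If enrolment has already begun, the revised card can still be used from dose 2. Dose 1 results for the added reactions should then be labelled as unsolicited for subjects who used the old card.
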